7.8 ADVERSE EVENTS MONITORING

Safety review will be performed at Pharma Mar S.A. once SAE forms have been received and the CRFs electronically completed by the Investigator.

At every monitoring visit performed by the designated clinical trial monitor, the consistency between the CRF/SAE data reported to the Pharmacovigilance Department and the patient's source data will be reviewed. In every case a discrepancy is found during the review, data will be amended/updated in the CRF and the SAE form/information reported to the Pharmacovigilance Department (when applicable), according to source data. An update (follow-up) with changes arisen will be signed by the Principal Investigator (or his/her designee) and then reported/provided to the Pharmacovigilance Department within 24 hours, with the CRF updated on the same dates.

Periodic safety review of clinical data will be performed. AEs will be monitored by the Investigators and by the study team at Pharma Mar S.A. The personnel in charge of this process are defined in the section "*Study Contacts*" of this protocol. Pharma Mar S.A. Pharmacovigilance Department will review the safety data of this trial on an ongoing basis.

SAEs will be continuously collected, assessed and reported throughout all the study as per the applicable Regulations by the Pharma Mar S.A. Pharmacovigilance Department. Periodic safety reviews of SAE reports are to be conducted and documented by the Pharmacovigilance Department.

As per the applicable regulations, Pharma Mar S.A. will report to the IECs/IRBs, Investigators and Competent Authorities:

- expedited: all serious, related, unlisted/unexpected AEs or critical safety findings (including those of special interest) from this and any other clinical trial with PM01183 and,
- periodic: all relevant safety information generated in all clinical trials with the IMP(s) within the Development Safety Update Report.

Non-serious AEs will be verified during monitoring visits by the monitor, who will discuss them with the Investigators, if applicable.

8. STATISTICAL METHODS

This phase II trial is designed to assess the antitumor activity of PM01183 in terms of ORR according to the RECIST v.1.1 assessed by IA in different selected advanced solid tumors: SCLC, H&N, NETs, biliary tract carcinoma, endometrial carcinoma, BRCA 1/2-associated metastatic breast carcinoma, carcinoma of unknown primary site, GCTs, and EFTs. In addition, in the SCLC cohort, tumor evaluation will be also done by IRC.

8.1 SAMPLE SIZE

Up to 25 evaluable patients in each tumor type will be recruited to test the null hypothesis that 1% or less patients get a response ($p \leq 0.01$) *versus* the alternative hypothesis that 10% or more patients get a response ($p \geq 0.10$). The variance of the standardized test is based on the null hypothesis. The type I error (alpha) associated with this one-sided test is 0.025 and the type II error (beta) is 0.2 (normal approximation; ~ 0.3 if exact binomial distribution); hence, statistical power is 80% (normal approximation; $\sim 70\%$ if exact binomial distribution). With these assumptions, if the number of patients who achieve a confirmed response is ≥ 2 , then this would allow the rejection of the null hypothesis.

An interim analysis to reject H0 (non-binding) or to reject H1 (futility) in each tumor type is planned after the recruitment of 15 evaluable patients in each cohort. The Gamma family boundary will be used to control the type I error, the parameter to reject H0 is fixed as -1 and the parameter to reject H1 is fixed as 0. If none of the first 15 evaluable patients in a determined cohort has a confirmed response, the alternative hypothesis will be rejected, according to boundaries and sample size assumptions, and recruitment will be stopped. If the number of responding patients is already two or more at the interim analysis, then H0 could be rejected and the study will have enough power to be stopped. On the contrary, if there is one confirmed response, the recruitment will be continued to up to 25 evaluable patients.

- A phase III trial of PM01183 combined with doxorubicin in SCLC is ongoing. Hence, the sample size for the SCLC cohort of this study will be expanded to 100 evaluable patients if the success boundary (≥ 2 confirmed responses) is reached in the first 25 evaluable patients.
- Based on the newly available information, additional patients will be recruited to test the null hypothesis that 15% or less patients get a response ($p \leq 0.15$) *versus* the alternative hypothesis that 30% or more patients get a response ($p \geq 0.30$). The variance of the standardized test is based on the null hypothesis. The type I error (alpha) associated with this one-sided test is 0.025 and the type II error

(beta) is 0.051 (normal approximation; ~0.05 if exact binomial distribution); hence, statistical power is 95% (normal approximation; ~95% if exact binomial distribution). With these assumptions, if the number of patients who achieve a confirmed response is ≥ 23 , then this would allow the rejection of the null hypothesis. The judgement of patient's evaluability and replacement of non-evaluable patients in each cohort for the interim analyses will be guided by the investigator assessment.

- A phase I trial of PM01183 combined with doxorubicin has shown encouraging antitumor activity in endometrial carcinoma. Hence, the sample size for the endometrial carcinoma cohort of this study will be doubled to 50 evaluable patients if the success boundary (≥ 2 confirmed responses) is reached in the first 25 evaluable patients.

Based on the newly available information, additional patients will be recruited to test the null hypothesis that 10% or less patients get a response ($p \leq 0.10$) versus the alternative hypothesis that 25% or more patients get a response ($p \geq 0.25$). The variance of the standardized test is based on the null hypothesis. The type I error (alpha) associated with this one-sided test is 0.025 and the type II error (beta) is 0.144 (normal approximation; ~0.16 if exact binomial distribution); hence, statistical power is ~86% (normal approximation; ~84% if exact binomial distribution). With these assumptions, if the number of patients who achieve a confirmed response is ≥ 10 , then this would allow the rejection of the null hypothesis.

With the sample size of 100 and 50 evaluable patients in each indication (SCLC and endometrial), the obtained confidence interval will be narrower and its half-width will be confined to $\pm 15\%$.

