6.2.1 Primary Endpoint

Exact binomial estimates with 95% confidence intervals (CIs) in each cohort will be calculated for the analysis of the main endpoint (ORR according to RECIST v1.1 by Investigator assessment)

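### The written two-stage rule for the 25-patient cohorts has 67% exact power at a 10% response rate, against a stated 80% (normal approximation) or about 70% (exact)

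*Protocol*

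**What the plan says.** Protocol 8.1 sets up each 25-patient cohort as a one-sided test of the "null hypothesis that 1% or less patients get a response" against the "alternative hypothesis that 10% or more patients get a response". On size, "Up to 25 evaluable patients in each tumor type will be recruited". On error rates, "The type I error (alpha) associated with this one-sided test is 0.025" and "the type II error (beta) is 0.2", the latter labelled as a normal approximation with an exact value of about 0.3 beside it. Power is given the same way: "hence, statistical power is 80" per cent by normal approximation, about 70% exact. Two or more confirmed responses reject the null. The synopsis and SAP 5.1 carry the same figures.

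The interim look is at 15 evaluable patients (Protocol 8.1 and 8.3, SAP 8.13). The futility side is mandatory: "If none of the first 15 evaluable patients in a determined cohort has a confirmed response, the alternative hypothesis will be rejected", and recruitment stops. With one response the cohort continues to 25. With two or more, stopping for success is optional. The boundaries are described as Gamma family, with parameter -1 for rejecting H0 and 0 for rejecting H1.

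The primary estimate is exact. SAP 6.2.1 says: "Exact binomial estimates with 95% confidence intervals (CIs) in each cohort will be calculated for the analysis of the main endpoint".

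**The concern.** The leading power figure rests on a normal approximation at a null rate where 25 patients yield 25 × 0.01 = 0.25 expected responses. The approximation is poor there, and the planned analysis does not use it. The exact figure beside it is loose, and nothing says whether it describes a single look at 25 patients or the rule with the interim stop.

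This matters when a negative cohort is read. Closing at 0/15 rejects the alternative for that tumor type. Anyone judging how much weight that carries needs the chance that a cohort with a true 10% response rate fails under the rule actually used.

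**Working it through.** **Inputs** (Protocol 8.1): p0 = 0.01, p1 = 0.10, maximum n = 25, one-sided alpha 0.025, null variance in the test, interim at 15 (information fraction 0.6), stop at 0/15, success at 2 or more.

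**1. Reproducing the 80%.** Fixed-sample normal approximation:
- n = (1.960·√0.0099 + 0.842·√0.09)² / 0.09² = 24.7, so 25.
- Power at n = 25: Φ[(0.09·√25 − 1.960·√0.0099) / √0.09] = Φ(0.85) = 80.2%.
- A group-sequential normal calculation with the stated Gamma boundaries gives 79.9%.

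The 80% therefore reproduces by the method it names, with or without the interim.

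**2. Do the Gamma boundaries give the count rule?** On the normal scale at 15 patients:
- Alpha spent with parameter -1: 0.025·(e^0.6 − 1)/(e − 1) = 0.0120, z = 2.258. Efficacy cut-off: 0.15 + 2.258·√(15·0.0099) = 1.02 responses.
- Beta spent with parameter 0: 0.2·0.6 = 0.12, z = −1.175. Futility cut-off: 1.5 − 1.175·√(15·0.09) = 0.13 responses.

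So 0 stops, 1 continues, and 2 or more rejects H0. This is the written rule.

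**3. Exact single-stage power** (2 or more of 25, no stop) at p = 0.10:
- 1 − 0.9^25 − 25·0.1·0.9^24 = 72.9%. Type I error at p = 0.01 is 0.0258.

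**4. Exact power of the written rule** at p = 0.10:

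| Outcome at 15 | Probability | Then | Contribution to power |
|---|---|---|---|
| 0 | 0.9^15 = 0.2059 | stop | 0 |
| 1 | 15·0.1·0.9^14 = 0.3432 | 1 or more of the next 10: 1 − 0.9^10 = 0.6513 | 0.2235 |
| 2 or more | 0.4510 | success | 0.4510 |

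- Power = 0.4510 + 0.2235 = 0.6745 (67.4% from unrounded values). Beta = 0.326, made up of 0.206 stopped at 0/15 and 0.120 with 1/15 then 0/10.
- The optional stop at 2 or more of 15 does not affect power, because two responses at 15 already secure two at 25.
- Type I error at p = 0.01: 0.0096 + 0.1303·(1 − 0.99^10) = 0.0221.

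**5. Where the gap comes from.**
- Normal to exact, single stage: 80.2 − 72.9 = about 7 points.
- The 0/15 stop: P(0/15)·P(2 or more of the next 10) = 0.2059·0.2639 = 5.4 points (72.9% to 67.4%).
- The other 20.6 − 5.4 = 15.2 points of cohorts stopped at 0/15 would have failed at 25 as well.

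**6. Comparison with the exact figures for the expanded cohorts.** In Protocol 8.1 these match single-stage calculations to the nearest point: P(10 or more of 50 at 0.25) = 83.6% (stated about 84%) and P(23 or more of 100 at 0.30) = 95.2% (stated about 95%). The figure of about 70% matches neither 72.9% nor 67.4% that closely.

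**The case against.** The strongest reply is that the plan discloses the problem. The sentence giving 80% labels it a normal approximation and gives about 70%, with beta about 0.3, for the exact binomial. Exact betas of 0.271 (single stage) and 0.326 (two stage) both round to 0.3. The trial is exploratory, type I error with the stop is inside 0.025, and no decision changes. All of this stands, and it limits the point to a restatement.

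Three stronger readings are tempting, and the documents do not support them.

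- A reader might infer that the 0/15 stop costs 21 points of power. The 20.6% is the probability of stopping at a true 10% rate. Most of those cohorts would have failed at 25 anyway, and the loss is 5.4 points.
- A reader might infer that the count rule departs from the Gamma boundaries, since parameter 0 allows 0.12 of beta at the interim (0.18 if beta is 0.3) while 0/15 exactly spends 0.206. That compares an exact probability with a normal-scale boundary. On the normal scale the boundaries reproduce the rule, and 0/15 is the least aggressive futility stop available at 15 patients. The Gamma statement should stay.
- A reader might infer that the 80% is a miscalculation, or that it leaves out the stop. It is neither shown to be: the group-sequential normal calculation with both boundaries gives 79.9%.

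The disclosure does not say which design the figure of about 70% describes. Nor can the written rule deliver the leading figure, because P(0/15) = 0.206 at a 10% rate by itself exceeds a beta of 0.2.

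**Conclusion.** The point holds as a modest, text-only correction. The written two-stage rule has exact power 67% at a 10% response rate, beta 0.33 and type I error 0.022. That is 12.6 points below the leading 80% and 2.6 points below the disclosed figure of about 70%; the second comparison is the fairer measure of what a careful reader is not told. If all seven cohorts capped at 25 had a true 10% rate, expected misses would be 7 × 0.326 = 2.3, against 2.1 at beta 0.3 and 1.4 at beta 0.2.

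This assumes independent responses at a common rate within a cohort, looks at exactly 15 and 25 evaluable patients, and a 0/15 stop that is always followed. If the stop were not enforced, exact power would be 72.9%, with type I error 0.0258.

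**What to change.** In the synopsis, Protocol 8.1 and SAP 5.1, replace the paired power figures with wording such as: *Exact power of the two-stage rule, including the 0/15 stop, is 67% (beta 0.33; type I error 0.022). Without the stop it would be 73%. The normal approximation gives 80%.* Add that a cohort with a true 10% response rate is stopped at 0/15 with probability 0.21.

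Keep the Gamma-boundary statement. Note beside it that the boundary was derived on the normal scale and that 0/15 spends 0.206 of beta exactly. The interim text is repeated in Protocol 8.3 and SAP 8.13, so the note should appear there too.

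No stopping rule, success threshold, sample size or analysis changes. The cost is an edit to three power statements and the interim text, and a stated power that looks less favourable.

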8.2 STATISTICAL ANALYSIS

Statistical analysis will be done by the Sponsor or under the authority of the Sponsor. The study protocol contains a general description; specific details will be provided in the Statistical Analysis Plan.

Frequency tables will be prepared for categorical variables, and continuous variables will be described by means of summary tables, which will include the median, mean, standard deviation, minimum, and maximum of each variable.

8.2.1 Efficacy Analyses

Counts and percentages, with their corresponding exact 95% confidence intervals, will be calculated for the binomial endpoints (e.g., ORR, clinical benefit). The confidence intervals based on the group sequential tests performed for each cohort will also be calculated.

Time-to-event variables (OS, PFS and DR) and their set time estimates (i.e., PFS 4/6 and OS 6/12) will be analyzed according to the Kaplan-Meier method.

In the SCLC cohort, the evaluation of the efficacy endpoints evaluated by IA and IRC will be analyzed and compared. The rate of concordance between both evaluation methods for best response, progression status and progression-free survival will be presented with 2-way frequency tables and measures of agreement.

Waterfall plots will be used to describe the best variation of the sum of target lesions during treatment.

The number of patients recruited in any cohort may differ from that pre-specified according to the sample size assumptions. Therefore, the main efficacy results will be calculated according to the planned cohort sample size and, if any cohort sample size differs at least 10% from the assumptions, a sensitivity analysis using all evaluable patients recruited (adjusting the corresponding boundaries to test the null hypothesis) will be performed.

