
STATISTICAL METHODS
	
This phase II trial is designed to assess the antitumor activity of PM01183 in terms of ORR according to the RECIST v.1.1 assessed by IA in different selected advanced solid tumors: SCLC, H&N, NETs, biliary tract carcinoma, endometrial carcinoma, BRCA 1/2-associated metastatic breast carcinoma, carcinoma of unknown primary site, GCTs, and EFTs. In addition, in the SCLC cohort, tumor evaluation will be also done by IRC.
 
Sample Size:
 
Up to 25 evaluable patients in each tumor type will be recruited to test the null hypothesis that 1% or less patients get a response ($p \leq 0.01$) versus the alternative hypothesis that 10% or more patients get a response ($p \geq 0.10$). The variance of the standardized test is based on the null hypothesis. The type I error (alpha) associated with this one-sided test is 0.025 and the

type II error (beta) is 0.2 (normal approximation; ~0.3 if exact binomial distribution); hence, statistical power is 80% (normal approximation; ~70% if exact binomial distribution). With these assumptions, if the number of patients who achieve a confirmed response is ≥ 2 , then this would allow the rejection of the null hypothesis.

Endometrial carcinoma:

Up to 50 evaluable patients will be recruited to test the null hypothesis that 10% or less patients get a response ($p \leq 0.10$) versus the alternative hypothesis that 25% or more patients get a response ($p \geq 0.25$). The variance of the standardized test is based on the null hypothesis. The type I error (alpha) associated with this one-sided test is 0.025 and the type II error (beta) is 0.144 (normal approximation; ~0.16 if exact binomial distribution); hence, statistical power is ~86% (normal approximation; ~84% if exact binomial distribution). With these assumptions, if the number of patients who achieve a confirmed response is ≥ 10 , then this would allow the rejection of the null hypothesis.

SCLC:

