3. OVERALL STUDY DESIGN

Multicenter, open-label, exploratory, phase II clinical trial to evaluate the efficacy and safety of PM01183 in previously treated patients with the following advanced solid tumors: SCLC, H&N, NETs, biliary tract carcinoma, endometrial carcinoma, BRCA 1/2-associated metastatic breast carcinoma, carcinoma of unknown primary site, GCTs, and EFTs.

Patients with each of the aforementioned tumors will be enrolled in nine cohorts. Up to 25 evaluable patients are planned to be enrolled in each cohort (50 in the endometrial carcinoma and 100 in the SCLC cohort). To consider that PM01183 has antitumor activity in any of the tumor types analyzed, at least two confirmed responses [complete (CR) or partial response (PR)] per RECIST v.1.1 out of the 25 patients of each cohort are expected.

- If no confirmed responses are observed in the first 15 evaluable patients of each cohort, the recruitment of the corresponding cohort will be stopped.
- If one confirmed response is observed in the first 15 evaluable patients of each cohort, the recruitment of this cohort will continue to up to 25 evaluable patients.

- o In the cohort of endometrial carcinoma, if ≥ 2 confirmed responses occur in the first 25 evaluable patients, the sample size will be doubled to 50 evaluable patients.
- o In the cohort of SCLC, if ≥ 2 confirmed responses occur in the first 25 evaluable patients, the sample size will be increased to 100 evaluable patients.
- If two confirmed responses are observed in the first 15 evaluable patients of each cohort, the recruitment of the corresponding cohort can be stopped.

Only in the SCLC cohort, an IRC will determine the best patient's response and assign the date of first documentation of response and progression/censoring according to RECIST v.1.1. Operational details for the IRC and the algorithm and its validation by an expert panel is described in detail in the IRC charter.

In addition, for safety reasons:

- If two patients have a treatment-related death in a cohort, the recruitment of the corresponding cohort will be stopped.
- If six patients have treatment-related deaths in the whole population, the study will be stopped.

Finally,

- A determined cohort can be early closed by the Sponsor in case of a low recruitment rate.

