15.2 SAP version history v2.0

After the second version of the SAP was approved, a new protocol "substantial amendment No. 6" and "Non-Substantial Amendment No.2" were included; therefore the SAP has been updated to version 3 in accordance with the new version of the protocol as follows:

- Study objectives. Assessment of antitumor activity by an Independent Review Committee (IRC) is included as a secondary objective in the small cell lung carcinoma (SCLC) cohort.
- Patient population. The maximum number of evaluable patients in this clinical trial is increased to 350 mainly because of the elevated recruitment in the endometrial carcinoma cohort, which exceeded in 20 patients the planned number, together with the increase in the SCLC cohort to 100 evaluable patients, and the re-opening of the metastatic breast carcinoma BRCA-positive cohort, which will recruit up to 25 patients. Consequently, clarification of the statistical analysis to be performed in case the number of evaluable patients included in any cohort of the study was higher than planned is incorporated.
- In order to have a deeper insight into the survival, the overall survival (OS), OS rate at 6 months and 12 months will be determined in each cohort.
- Other not relevant minor comments/clarifications.

Detailed changes are presented in the next pages. Changes are highlighted in *Italic bold* and text removed has been ~~crossed-out~~.

Any changes in the automatic numbering of tables, sections and references in the SAP are not listed but will be implemented in the new version.

Section 1: Rationale

Original text:

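### Does the plan need to name the method for adjusting the response boundary when a 25-patient cohort ends at a different size?

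*Protocol*

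**What the plan says.** Protocol 8.1 and SAP 5.1 set up the 25-patient cohorts with a "null hypothesis that 1% or less patients get a response" against "the alternative hypothesis that 10% or more patients get a response", at one-sided 0.025, with two or more confirmed responses rejecting the null. The test is a standardized one: "The variance of the standardized test is based on the null hypothesis". Power is given on two scales: "hence, statistical power is 80% (normal approximation; ~70% if exact binomial distribution". Protocol 8.3 and SAP 8.13 add a look at 15 evaluable patients with Gamma-family boundaries (parameter -1 to reject the null): none of 15 stops the cohort, one continues it, and two or more may stop it for success.

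SAP 6.2.1 says how the endpoint is estimated: "Exact binomial estimates with 95% confidence intervals (CIs) in each cohort will be calculated for the analysis of the main endpoint".

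For cohorts that miss their target, Protocol 8.2.1 (repeated in the synopsis and SAP 6.2) keeps the main results at the planned size. If the departure is at least 10%, it adds that "a sensitivity analysis using all evaluable patients recruited (adjusting the corresponding boundaries to test the null hypothesis) will be performed". Nothing states the recalculation method. SAP 8.11 mentions the same sensitivity analysis without boundaries.

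**The concern.** A 10% departure from 25 means 22 or fewer, or 28 or more. Small cohorts are possible because Protocol section 3 provides that "A determined cohort can be early closed by the Sponsor in case of a low recruitment rate". Large ones are possible too: SAP 15.2 records endometrial recruitment "which exceeded in 20 patients the planned number".

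With a null rate of 1% and so few patients, the normal approximation is poor, and one response more or less decides the test. If the adjusted boundary came from the standardized test, a cohort closed at 12 with one response would reject the null. If it came from the exact binomial distribution, it would not. The reverse worry arises at 28, where two responses pass on one basis and fail on the other. Because the trial is open-label, an unstated method could in principle be picked once the responses are known. The exact power of about 70% also does not say whether the stop at 0 of 15 is counted.

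**Working it through.** **Inputs.** p0 = 0.01, p1 = 0.10, one-sided alpha 0.025, null variance, n = 25, success at 2 or more (Protocol 8.1); look at 15, stop at 0 of 15, Gamma(-1) (Protocol 8.3).

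**The plan's own figures.** Normal cut-off: 25 × 0.01 + 1.96 × √(25 × 0.0099) = 0.25 + 0.975 = 1.225, so 2 responses. Normal power: Φ[(2.5 − 1.225)/√(25 × 0.09)] = Φ(0.85) = 80.2%, matching the stated 80%.

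Exact power at 10%:
- No stop: P(X ≥ 2 of 25) = 72.9%.
- With the 0/15 stop: P(X15 ≥ 2) + P(X15 = 1) × P(X10 ≥ 1) = 0.4510 + 0.3432 × 0.6513 = 67.4%.

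Both round to about 70%. The exact one-sided error of 2 or more at 25 is 0.0258 without the stop and 0.0221 with it.

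**Small cohorts, one response.** z = (1/n − 0.01)/√(0.0099/n). The Gamma(-1) bound is taken at fraction n/25, which is an assumption, since the plan defines no look there.

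| n | z | Gamma(-1) bound | exact error, ≥1 | exact error, ≥2 |
|---|---|---|---|---|
| 5 | 4.27 | 2.72 | 4.9% | 0.1% |
| 10 | 2.86 | 2.45 | 9.6% | 0.4% |
| 12 | 2.55 | 2.37 | 11.4% | 0.6% |
| 14 | 2.31 | 2.29 | 13.1% | 0.8% |
| 15 | 2.21 | 2.26 | 14.0% | 1.0% |

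One response therefore crosses the normal-theory bound up to 14 and no longer at 15. At n = 3 the exact error of one response is already 2.97%, so the range of disagreement is 3 to 14. From 16 to 22, with the look at 15 kept, both bases ask for two.

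The exact 95% interval for 1 of 12, which SAP 6.2.1 requires, runs from 0.21% to 38.5% and contains 1%.

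**Large cohorts.** At 28, two responses give z = 3.27 against a re-derived Gamma final bound of 2.07, so two suffice on the normal basis. Exact figures, counting the 0/15 stop:

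| rule at 28 | one-sided error | power at 10% |
|---|---|---|
| 2 or more | 0.0256 | 70.7% |
| 3 or more | 0.0025 | 51.3% |

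The error of 2 or more is 0.0244 at 27, 0.0279 at 30 and 0.0334 at 35.

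This two-stage exact calculation is not described in the plan. A single-stage exact test already asks for three responses at the planned 25 (0.0258 exceeds 0.025, and the exact lower limit for 2 of 25 is 0.98%). The exact interval was therefore never the source of the planned boundary.

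**The case for a change.** The best argument for a change is that a cohort closed at 12 has no planned-size result to fall back on, so the adjusted boundary is the only formal one that fits. A normal-theory boundary there has more than four times its nominal error (11.4% against 2.5%). The protocol defers details to the SAP, and the SAP repeats the protocol's sentence. Naming a method would add no patients.

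The omission and the arithmetic stand. The consequence is weaker. The two-response minimum in Protocol section 3 is worded for 25 patients, but an analyst who is told that one response in 15 means carry on would not read one in 12 as success, and the exact interval printed beside it would contradict the claim. SAP 6.2.1 concerns estimation and sets no competing test. The only boundary method the plan names is the Gamma family.

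Above plan, three responses at 28 would be harder to reach than two at 25 (51.3% against 67.4%), so naming the exact basis would not be a cost-free edit. The one recorded departure is in the endometrial cohort (null 10%, target 50), to which none of these thresholds apply. Nothing in the documents suggests that a method would be chosen after seeing responses.

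**Conclusion.** The plan leaves the recalculation method unstated, and for a null rate of 1% the choice can change a cohort's verdict at 3 to 14 evaluable patients and from 28 upward. No change is needed. The rule feeds a sensitivity analysis; the results at 25 and the look at 15 do not depend on it.

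In small cohorts, the design's two-response minimum and the exact interval lead an analyst to the sensible answer. In larger ones, two or three responses is a fair trade-off: at 28 the excess error is 0.0006, and removing it costs 70.7 − 51.3 = 19.4 points of power at a 10% response rate. The excess grows with size (0.0334 − 0.025 = 0.0084 at 35), but the documents report no 25-patient cohort of that size. About 70% is a fair rounding of either exact power figure.

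This rests on three assumptions: the look at 15 is kept, no continuity correction is used (none is mentioned), and the adjusted boundary stays a sensitivity result.
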